**SYNOPSIS**

|  |
|--|
| Name of Sponsor/Company: Hill Dermaceuticals, Inc.  |
| Name of Finished Product: Miconazole oil  |
| Name of Active Ingredient: 2% miconazole  |
| Study Title:
Dose-Ranging Study of the Efficacy and Safety of Miconazole Oil Used for 7 or 14 Day Compared with Vehicle in the Treatment of Otomycosis   |
| Study Number: HD-MCZ-PHI-DRF062016  |
| Study Center(s): Up to 10 study centers in the United States (US)   |
| Number of Subjects Planned: Approximately 75  |
| Study Period:
The study duration for each subject will be up to 30 days (up to 14 days of treatment, and 8 days of follow-up, including the visit window of up to 8 additional days after the scheduled day to complete the final visit)   |
| Phase of Development: 2   |
| Objectives: 

• Obtain preliminary evidence of the efficacy and safety of miconazole oil compared with vehicle over a 14-day treatment duration

• Descriptively compare the efficacy and safety of miconazole oil over 7 versus 14 days

   |
| Design and Methodology:
This study is a randomized, partially masked, multiple-dose, parallel-group design study conducted at up to 10 study centers in the US. Approximately 75 male or female subjects with otomycosis will receive study drug. Subjects will be randomly assigned in a 1:1:1 ratio to receive miconazole oil [administered as 5 drops per ear at ~30 mg per drop instilled into the external ear canal of the ear(s) affected by otomycosis] for 7 or 14 days, or vehicle for 14 days. During the study it is planned to assess treatment allocation to ensure that there is a sufficient number of subjects within each group for the primary analysis. If deemed necessary, future randomizations may be adjusted. For subjects assigned to the 14-day treatment duration with either miconazole oil or vehicle, the contents of the study drug will be masked to both the subject and the investigator and study staff (i.e., double-blind), but the treatment duration assigned to each subject (7 or 14 days) will be unmasked to both the subject and the investigator and study staff.
At Screening/Baseline (Day 1), potentially eligible subjects will provide informed consent, and subjects will undergo screening evaluations to include a physical examination, an assessment of the signs and symptoms of otomycosis (pruritus, debris, visual examination for presence of fungal elements, and pain), and an evaluation of medical history. Urine will be obtained for pregnancy screening in female subjects of childbearing potential. Prior and concomitant medications will be reported. Subjects with positive signs and symptoms of otomycosis and who meet all other eligibility criteria will be entered into the study, and a subject global assessment of disease will be performed. Fungal and bacterial cultures of the affected ear(s) will be taken, then debris will be cleaned from the affected ear(s) following the site's normal procedures. The subject will then begin treatment with study drug. The subject or caregiver will instill the first dose of study drug at the site, under the supervision of the investigator or site personnel. Adverse events (AEs) will then be assessed. The subject will then leave the clinic and continue to administer the study drug twice per day as instructed. Subjects will be instructed to avoid getting water in the ear, to consider drying excessive water in the ear by |

|  |
|--|
| Name of Sponsor/Company: Hill Dermaceuticals, Inc.  |
| Name of Finished Product: Miconazole oil  |
| Name of Active Ingredient: 2% miconazole  |
| using a blow dryer, and to place a Vaseline-impregnated cotton ball over the affected ear(s) to help keep water out of the ear while bathing or showering.   |
| All subjects will return to the clinic on Day 8. For subjects randomized to the 7-day treatment duration, this visit will constitute the End of Treatment Visit, with procedures performed as described for that visit below. Subjects randomized to 7-day treatment will not administer study drug on Day 8. For all other subjects, for whom this visit will constitute an On Treatment Visit, a clinical evaluation of the signs and symptoms of otomycosis, a subject global assessment, a cleaning of the affected ear(s) (following the site's normal procedures), and an assessment of AEs and concomitant medications will be performed, and these subjects will continue to administer the study drug twice per day, up through Day 14, following the same instructions as provided at the Screening/Baseline Visit on Day 1. |
| All subjects will return to the clinic on Day 15. For subjects randomized to the 7-day treatment duration, this visit will constitute the Test of Cure Visit, with procedures performed as described for the Test of Cure Visit below. For subjects randomized to the 14-day treatment duration, this visit will constitute the End of Treatment Visit, with procedures performed as described for the End of Treatment Visit below.   |
| Subjects randomized to the 14-day treatment durations will return to the clinic on Day 22, for the Test of Cure Visit, with procedures performed as described for the Test of Cure Visit below. Procedures performed at the End of Treatment Visit will include an assessment for clinical signs and symptoms of otomycosis, a subject global assessment, and a fungal culture of the affected ear(s). For subjects randomized to the 7-day treatment duration, subjects will have the affected ear(s) cleaned according to the site's normal procedures at this visit, after the efficacy procedures have been completed. AEs and concomitant medications will also be assessed, and the subject will return all unused study drug.   |
| Procedures performed at the Test of Cure Visit will include an assessment of clinical signs and symptoms of otomycosis, a subject global assessment, and a fungal culture of the affected ear(s). AEs and concomitant medications will also be assessed. A urine pregnancy test will be performed in women of childbearing potential.  |
| Study Visits:
Screening/Baseline (1 visit); On Treatment (up to 1 visit); End of Treatment (1 visit); Test of Cure (1 visit)   |
| Efficacy Evaluations: 

• Clinical signs and symptoms of otomycosis (pruritus; debris; presence of fungal elements; pain)

• Fungal culture

• Subject global assessment

  |
| Safety Evaluations: 

• AEs

   |

**Name of Sponsor/Company:** Hill Dermaceuticals, Inc.

**Name of Finished Product:** Miconazole oil

**Name of Active Ingredient:** 2% miconazole

**Key Inclusion Criteria:**

Male or non-pregnant, non-lactating females with a clinical diagnosis of uncomplicated otomycosis of the external ear only, with an intact tympanic membrane, who are in general good health as determined by medical examination and medical history, and who are free of clinically significant disease, including diabetes mellitus, that is not well-controlled or that could interfere with the study, will be included in the study.

**Key Exclusion Criteria:**

Subjects with any other dermatoses or conditions of the ear that may interfere with the evaluation of otomycosis, including concomitant otic infections (including bacterial infection) that require antimicrobial treatment, disease that has spread beyond the external ear(s), or pre-existing skin atrophy of the affected ear(s); tympanostomy tube or perforated tympanic membrane in the ear(s) that will be treated with study drug; history of prior surgery directly affecting and compromising the external auditory canal and/or tympanic membrane of the ear(s) that will be treated with study drug, except for prior tympanostomy tube(s) that have already been removed and completely healed; use of any topical medicated treatments for otomycosis within 14 days of study entry; use of any systemic antifungal therapy within 28 days of study entry, warfarin within 28 days of study entry, immunosuppressive or immune-stimulating drugs within 28 days of study entry, or systemic steroids within 3 months of study entry; fever of  $\geq 100^{\circ}\text{F}$  at study entry; recurrent otomycosis that has been unresponsive to previous antifungal treatment; known hypersensitivity to any of the components in the test formulation; and participation in another investigative trial within 28 days of study entry will be excluded from the study.

**Test Product, Dose, and Mode of Administration:**

Miconazole oil (7-day and 14-day treatment durations)

Active ingredient: 2% miconazole

Other ingredients: refined peanut oil, mineral oil, oleth-2, and isopropyl myristate

Mode of administration: subjects will be seated and then instructed to tilt their heads so that the affected ear is facing up. The subject or caregiver will then gently pull the ear lobe backward and upward and apply 5 drops of miconazole oil into the ear. The subject will be instructed to keep the head tilted with the ear facing up for approximately 1 minute to allow the miconazole oil to penetrate lower into the ear canal. If both ears are being treated, the process will then be repeated for the other ear after a 5-minute wait.

**Reference Product, Dose, and Mode of Administration:**

Vehicle (14-day treatment duration)

Active ingredient: none (vehicle group)

Other ingredients: refined peanut oil, mineral oil, oleth-2, and isopropyl myristate

Mode of administration: same as described for the test product.

**Statistical Analyses:**

The primary and secondary endpoints will be based on the investigator reporting of signs and symptoms. Other efficacy endpoints will be based on the subject reporting of the symptom of pruritus.

Descriptive statistics will be presented for the signs and symptoms of otomycosis for the study ear at each evaluation and will include the number and percentage of subjects in each category. Subject assessments for the study ear for pruritus will also be summarized. No

|  |
|--|
| Name of Sponsor/Company: Hill Dermaceuticals, Inc.  |
| Name of Finished Product: Miconazole oil  |
| Name of Active Ingredient: 2% miconazole  |
| imputation will be made for missing data.  |
| The primary efficacy endpoint will be the percentage of subjects at the Test of Cure Visit with “therapeutic cure,” defined as a negative mycological culture plus “clinical cure.” Clinical cure is defined as the absence of all otomycosis signs and symptoms according to the scales for each individual sign or symptom and with absence defined as a score of 0 on each of the scales for pruritus, debris, fungal elements, and pain.   |
| Other efficacy endpoints will include:   |
| 

• Percentage of subjects with clinical cure at the Test of Cure Visit

• Percentage of subjects with a negative fungal culture at the Test of Cure Visit

• Percentage of subjects with a negative fungal culture at the Test of Cure visit as well as individual sign or symptom score of 0 or 1 on each of the scales for pruritus and debris and a score of 0 on each of the scales for fungal elements and pain.

• Percentage of subjects with individual signs or symptoms with a score of 0 or 1 on each of the scales for pruritus and debris and a score of 0 on each of the scales for fungal elements and pain.

• Subject global assessments at Baseline and Test of Cure as well as categorical shifts in the subject global assessment scale scores from the Screening/Baseline to the Test of Cure Visit

• If feasible, analyses may also be conducted by fungal organism isolated at Screening/Baseline.

 |
| The primary population for all efficacy analyses will be the modified intent-to-treat (MITT) population, defined as all subjects who were randomized, dispensed study drug, and with a clinical diagnosis of otomycosis confirmed by a positive fungal culture.  |
| In cases of bilateral otomycosis, the ear with the worse infection at Screening/Baseline, as assessed by the investigator by taking into account both clinical signs and symptoms and fungal culture results, will be used as the study ear for efficacy analyses. If both ears are determined by the investigator to have the same degree of infection at Screening/Baseline, the left ear will be used as the study ear for the purposes of efficacy analyses.   |
| The primary population for all safety analyses will be the safety population, defined as all randomized subjects who received at least one dose of study drug and had at least one post-Baseline safety assessment.  |
| All AEs occurring during the study will be recorded and classified using terminology from the Medical Dictionary for Regulatory Activities (MedDRA). All reported treatment-emergent adverse events (TEAEs), defined as any AE with an onset on or after the date of first study drug application, will be summarized by treatment group. Summaries will provide the number of subjects reporting TEAEs, system organ class, preferred term, severity, and relationship to study drug. When summarizing TEAEs by severity or relationship to study drug, each subject will be counted only once within a system organ class or a preferred term using the event with the greatest severity or causality, respectively, within each category. All reported SAEs will be summarized by the number of subjects reporting the event, system organ class, preferred term, severity, and relationship to study drug.   |
| All efficacy and safety analyses and comparisons between groups will be descriptive in nature, with no formal hypothesis testing performed.  |

|   |
|---|
| Name of Sponsor/Company: Hill Dermaceuticals, Inc.   |
| Name of Finished Product: Miconazole oil   |
| Name of Active Ingredient: 2% miconazole   |
| Sample Size:
The sample size for this study is not based on statistical considerations and is instead intended to be a reasonable number of subjects upon which to gather preliminary information on the efficacy and safety of miconazole oil when administered via the otic route to subjects with otomycosis.  |
| Interim Treatment Allocation Assessment(s):
A subject's MITT status (specifically positive fungal culture at baseline) is determined only following randomization, which may result in imbalance between treatment groups. Therefore, at least one assessment during the conduct of the study is planned to ensure that there is a sufficient number of subjects within each group for the primary analysis. Once at least 10 MITT subjects have been enrolled in the 7-Day active group, the numbers of MITT subjects in the 14-Day active group and the 14-Day vehicle group will be determined by an unblinded statistician; no persons involved in the day to day conduct of the study will be unblinded. Randomization allocation for future subjects may be adjusted if deemed necessary to achieve minimum number of subjects within each arm. |

**LIST OF ABBREVIATIONS**

| Abbreviation | Definition                     |
|----------------------------|--|
| AE                         | Adverse event                                |
| eCRF                       | Electronic case report form                  |
| EDC                        | Electronic data capture                      |
| FDA                        | Food and Drug Administration                 |
| GCP                        | Good Clinical Practice                       |
| ICH                        | International Conference on Harmonisation    |
| IRB                        | Institutional review board                   |
| ITT                        | Intent-to-treat                              |
| IUD                        | Intrauterine device                          |
| LOCF                       | Last Observation Carried Forward             |
| MedDRA                     | Medical Dictionary for Regulatory Activities |
| MIC                        | Minimum inhibitory concentration             |
| MITT                       | Modified intent-to-treat                     |
| OTC                        | Over the counter                             |
| PP                         | Per protocol                                 |
| SAE                        | Serious adverse event                        |
| TEAE                       | Treatment-emergent adverse event             |
| US                         | United States                                |

## 1 INTRODUCTION

### 1.1 Brief Background Information

Miconazole is an imidazole antifungal agent that has been available by prescription and over the counter (OTC), in different formulations, for many years. It is commonly used for different types of fungal skin infections, such as *Candida*, ringworm, jock itch, athlete's foot, nail fungus, vaginal yeast infections, and oropharyngeal candidiasis. Formulations containing up to 4% miconazole nitrate have been approved for OTC use as topical antifungal agents in cream, ointment, powder, or gel dosage forms. The 2% formulation is commonly used for dermatophytic infections.

While antifungal agents including miconazole are used in practice for the treatment of fungal otitis externa (also called otomycosis), there are currently no treatments approved by the United States (US) Food and Drug Administration (FDA) for this indication in humans. Miconazole is currently FDA-approved as a component of two veterinary combination products (Surolan and Easotic) administered topically to dogs for the treatment of canine otitis externa caused by susceptible strains of yeast and bacteria. Each veterinary product contains miconazole in combination with an antibacterial agent and a corticosteroid. The concentration of miconazole present in Surolan (23 mg/mL miconazole nitrate) is similar to the 2% concentration of miconazole planned for use in humans in this study. The concentration of miconazole present in Easotic is 15.1 mg/mL miconazole nitrate, which equates to approximately 1.5% miconazole. While the causative organism of canine otitis externa, *Malassezia pachydermatis*, is not typically associated with human otomycosis in the US, it is expected that human otomycosis, which is most commonly associated with organisms from the *Candida* and *Aspergillus* genera, would respond to concentrations of miconazole similar to those used in dogs.

The mechanisms of action of miconazole when used topically for the treatment of fungal infections involve its actions against the fungal organisms, rather than their human host. Miconazole targets the cytochrome P450-dependent enzyme 14- $\alpha$ -sterol demethylase, an enzyme that is also involved in mammalian cholesterol synthesis, resulting in inhibition of ergosterol biosynthesis in the cell membrane. Because ergosterol is an important component of the cell membrane, inhibition of its synthesis inhibits fungal cell growth [Vandenbosch 2012]. In addition to its activity toward the enzyme 14- $\alpha$ -sterol demethylase, miconazole also leads to increased reactive oxygen species in fungal organisms, which appears to result in fungicidal activity [Vandenbosch 2010; Musaji 2010].

The mechanisms of action of miconazole against fungi in general appear to be applicable to fungi associated with otomycosis, in that miconazole has been demonstrated to have activity against some clinical isolates of fungi associated with human otomycosis in the US *in vitro* [Bassiouny 1986; Stern 1988]. Clinical studies of 2% miconazole conducted outside of the United States also suggest the efficacy of miconazole in the treatment of human otomycosis [Kiakojuri 2007; Vennewald 2010; Navaneethan 2015].

The purpose of this study is to gather preliminary data on the efficacy and safety of 2% miconazole oil after topical otic administration in subjects with otomycosis. A 14-day regimen of

twice-daily administration of 2% miconazole oil will be descriptively compared with the same treatment regimen using the product vehicle. Furthermore, the 14-day regimen of 2% miconazole oil will be compared with a 7-day regimen, to gather preliminary dose-ranging data regarding the duration of treatment. The 2% concentration of miconazole is selected for this study due to the results of an internal study conducted by the sponsor *in vitro* demonstrating greater zones of inhibition against *Candida* and *Aspergillus* using the 2% concentration compared with the 1% concentration. Furthermore, the 2% miconazole concentration is commonly used for dermatophyte infections, and topical application is expected to be  $\geq 1000$ -fold the minimum inhibitory concentrations (MICs) of the *Candida* and *Aspergillus* organisms most commonly associated with human otomycosis in the US.

## **1.2 Compliance with Good Clinical Practice**

The investigator and all study staff will conduct the study in compliance with this protocol and FDA regulations, all applicable federal, state, and local laws, rules and regulations relating to the conduct of a clinical study, the ethical principles of the Declaration of Helsinki, and the current International Conference on Harmonisation (ICH) Good Clinical Practice (GCP) guidelines.

## **1.3 Justification of the Study, Risks, Dose, and Inclusion of Subjects with Peanut Allergy**

### **1.3.1 Study and Risks**

Miconazole has been approved by the US FDA since 1974 and achieved OTC status for some indications when FDA issued a final monograph for miconazole on September 23, 1993. Miconazole is FDA-approved as a prescription for other indications. Approved routes of administration in humans have included systemic (intravenous) routes, as well as a variety of topical routes (dermatologic, intravaginal, and buccal).

Miconazole has not been FDA-approved for otic administration for any indication in humans, but clinical studies in other countries of otically-administered miconazole have been conducted and support the efficacy of miconazole in the treatment of otomycosis [Kiakojuri 2007; Vennewald 2010; Navaneethan 2015]. *In vitro* evidence exists of the susceptibility of clinical isolates from patients with otomycosis to miconazole, including one study of isolates from patients with otomycosis in the US [Bassiouny 1986; Stern 1988]. These results, along with the potential complications of untreated otomycosis, suggest a potential benefit to patients to study miconazole administered otically for the treatment of otomycosis.

The safety of miconazole as a topical dermal application is supported by its OTC approval for dermal conditions. Side effects of topical application to the skin may include blistering, burning, redness, skin rash, or other sign of skin irritation [PubMed Health 2015]. Side effects mentioned in the Monistat 1 consumer information leaflet include burning, itching, irritation, swelling, hives, skin rash, abdominal pain, and abdominal cramping. Other possible local effects of miconazole which may provide benefit in otomycosis may include anti-inflammatory activity at the skin, and possible restoration of skin barrier function in some circumstances of skin injury [Xhauflaire-Uhoda 2006; Liebel 2006].

Evidence supporting the safety of miconazole administered by the otic route comes largely from nonclinical studies. The possibility exists that miconazole could access the middle ear through the tympanic membrane, then diffuse through the round window membrane of the middle ear to reach and damage the cochlea. Miconazole appeared to be non-ototoxic when instilled at a 2% concentration directly into the round window niche of guinea pigs three times over the course of a week [Tom 2000]. Miconazole oil, instilled at 1% and 2% concentrations to guinea pigs twice daily over a period of 14 days in a nonclinical study conducted by the sponsor, also generally failed to demonstrate ototoxicity, although minor hair cell loss was observed in 1 animal in each of the 1% and 2% miconazole groups. Bilateral hearing loss, as assessed by increases in auditory brainstem responses, was observed in all animals in the miconazole vehicle group as well as in each of the 1% and 2% miconazole groups, but not in the saline control group. These results suggest that the hearing loss was due to the miconazole oil vehicle, rather than the miconazole itself. Because this hearing loss was generally not associated with hair cell loss, it is believed that this hearing loss was caused by instillation of a relatively large volume of product in a small animal (resulting in physical blockage of conduction), rather than actual damage to the ear caused by miconazole or the miconazole vehicle. Refer to the Investigator's Brochure (IB) for miconazole oil [[Investigator's Brochure for miconazole oil 2016](#)] for more information on the 14-day study of miconazole oil in guinea pigs.

The bilateral hearing loss observed in guinea pigs after a 14-day treatment with miconazole oil and its vehicle is not expected to occur in humans at the doses and volumes of study drug planned for clinical use. The miconazole oil vehicle is almost identical to that of another product manufactured by the sponsor and approved for topical otic administration (DermOticTM, containing 0.01% fluocinolone acetonide and used for the treatment of chronic eczematous external otitis). No subjects randomized to the DermOtic group of the clinical studies reported hearing loss, and no post-marketing reports of hearing loss have been received since DermOtic's approval in 2005.

The non-ototoxicity of the active ingredient, miconazole, is also supported in another species of animal by FDA approval of miconazole in two combination products (Surolan, which contains approximately 2% miconazole, and Easotic, which contains approximately 1.5% miconazole) administered by the otic route for the treatment of canine otitis externa caused by susceptible strains of yeast and bacteria. In the studies of Surolan in which hearing loss was assessed, hearing loss was only reported in 3 of 161 dogs (1.9%) and with apparent reversibility in the 2 dogs for which follow-up information was available and normal hearing was demonstrated at a later date.

Systemic effects of miconazole are generally not expected after topical otic administration. Systemic absorption of miconazole and distribution to locations other than the skin have been demonstrated to be low after topical dermal administration, as has been reported for other miconazole-containing products such as the VusionTM topical ointment used for the treatment of diaper dermatitis complicated by candidiasis in children. Thus, although some potential systemic effects of miconazole have been reported and the liver has been identified in prior FDA miconazole product approvals to be the main toxicological target of systemic miconazole; these effects are generally not expected after topical otic administration of the doses planned for this study.

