#### 7.4.2 Debris

Upon otoscopic examination, the investigator will score the amount of debris present in each ear being treated with study drug. Scores will be according to the following scale:

| Score | Category | Description  |
|-------|----------|--|
| 0     | None     | No debris present  |
| 1     | Scant    | Debris minimally present, but with no notable occlusion of external ear canal                    |
| 2     | Moderate | Debris present with partial occlusion of external ear canal; tympanic membrane can be visualized |
| 3     | Heavy    | Complete occlusion of ear canal; tympanic membrane cannot be visualized                          |

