## 8 ADVERSE EVENTS

### 8.1 Definition of an Adverse Event

An AE is any untoward medical occurrence in a subject or clinical investigation subject administered a study drug and which does not necessarily have a causal relationship with the study drug. An AE can therefore be any unfavorable and unintended sign (including a clinically significant abnormal laboratory finding), symptom, or disease temporally associated with the use of an investigational or marketed study drug, whether or not considered related to the investigational or marketed study drug. AEs include any illness, sign, or symptom that has appeared or worsened during the course of the clinical trial, regardless of causal relationship to the study drug. Study drug includes the investigational drug under evaluation and the comparator product.

Medical conditions/diseases present before signing the informed consent form are only considered AEs if they worsen after the informed consent form is signed.

AEs may be either spontaneously reported or elicited during questioning and examination of a subject. At each examination or visit, study personnel will ask each subject the following question, "Have you had any problems since we last spoke?" If known, the investigator should report the diagnosis of the underlying illness or disorder, rather than its individual symptoms.

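### Every arm receives the oil that the protocol links to hearing loss in guinea pigs, but hearing is never asked about, so zero reports would be weak evidence

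*Protocol*

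**What the plan says.** **The signal.** Protocol 1.3.1 reports a sponsor study in guinea pigs, dosed twice daily for 14 days. Hearing loss (auditory brainstem responses were the measure) "was observed in all animals in the miconazole vehicle group as well as in each of the 1% and 2% miconazole groups, but not in" animals given saline. The protocol concludes: "These results suggest that the hearing loss was due to the miconazole oil vehicle, rather than the miconazole itself". On mechanism, "it is believed that this hearing loss was caused by instillation of a relatively large volume of product in a small animal", and the loss was generally not accompanied by hair cell loss.

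**The expectation in humans.** The finding "is not expected to occur in humans at the doses and volumes of study drug planned for clinical use". The support is a marketed otic product in an almost identical vehicle: "No subjects randomized to the DermOtic group of the clinical studies reported hearing loss", and there have been no post-marketing reports. Protocol 1.3.2 adds that this product is also given as 5 drops.

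**The arms.** Protocol 9.1 and 9.2: miconazole oil for 7 days, miconazole oil for 14 days, or the oil vehicle for 14 days. No arm is free of oil.

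**What is collected.** Safety is adverse events only (Protocol section 3 and 10.1.4; SAP 5.2). The standard question at each visit is "Have you had any problems since we last spoke". Protocol 8.1 also allows events to be elicited by questioning and examination, and 8.4 records which ear is affected. Conditions present before consent "are only considered AEs if they worsen after the informed consent form is signed". Table 1, the visit lists (6.2 to 6.4), the pruritus and pain scripts (7.4.1, 7.4.4), the global assessment (7.5) and the SAP tables contain no hearing item.

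**The concern.** Preliminary safety evidence is one of the study's objectives, and Protocol 1.3.1 says that otic safety evidence for miconazole is largely nonclinical. Hearing loss is the otic risk the protocol discusses at most length, and it is tied to the component that all arms share. The masked 14-day comparison of active with vehicle isolates miconazole and cannot show an effect of the vehicle. What remains is mainly each subject's own change, and nothing prompts sites to establish the starting point.

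The starting point matters because the disease can itself block the canal. A debris score of 3 is "Complete occlusion of ear canal; tympanic membrane cannot be visualized", and nothing in the eligibility criteria excludes that score. If a subject mentions poor hearing on Day 8, the site may be unable to say whether it is new. If nobody mentions it, the final safety tables could be taken to support the protocol's expectation although no one was asked.

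**Working it through.** **1. Is hearing sought anywhere?** The places where it could appear are these.

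| Place | What it provides |
|---|---|
| Protocol Table 1, 6.2 to 6.4 | No hearing item at any visit |
| Protocol 7.1, 7.2 | Full medical history and baseline examination that includes ears; no hearing prompt |
| Protocol 7.4.1, 7.4.4, 7.5 | Scripts on itch, pain and discomfort only |
| Protocol 7.4.2 | Otoscopic debris score 0 to 3 at every visit, used for efficacy |
| Protocol 8.1, 8.4 | Open adverse event question; affected ear recorded |
| SAP Listing 16.2.4.2.2 | Medical history, with a column for examination findings |
| SAP Listing 16.2.4.3 | Whether the examination was performed, no findings |

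Known or volunteered hearing loss therefore has places to be recorded. Nothing ensures that it is.

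**2. Is there any between-arm information on the oil?** The 7-day arm stops after Day 7 and the 14-day arms continue through Day 14. All arms are cleaned at Day 8 and seen at Day 15, so events arising between those visits compare stopped with continued oil. Under 1:1:1 allocation of 75 this is 75/3 = 25 against 2 × 25 = 50 subjects. It is not masked, because treatment duration is open.

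**3. How informative would silence be?** The only hearing-loss rate in the documents is in Protocol 1.3.1: 3/161 = 1.86%, which reproduces the stated 1.9%. It comes from dogs given a product that combines miconazole with an antibacterial and a corticosteroid (Protocol 1.1), so it is not a rate for this vehicle. It serves here only as an illustration, beside an assumed rate of 10%. The share *r* of true cases that subjects volunteer is not in the documents and is assumed to lie between 10% and 100%.

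- Chance of at least one report among 75: 1 − (1 − r × p)^75. For r = 0.25 and p = 3/161: 1 − (1 − 0.00466)^75 = 29.5%.
- One-sided 95% upper limit on the true rate after zero reports: (1 − 0.05^(1/75)) / r = 3.9% / r.

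| r (assumed) | P(≥1 report), p = 1.86% | P(≥1 report), p = 10% | Upper limit after 0 reports |
|---|---|---|---|
| 100% | 76% | >99.9% | 3.9% |
| 50% | 50% | 98% | 7.8% |
| 25% | 30% | 85% | 15.7% |
| 10% | 13% | 53% | 39% |

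A common and noticeable effect would probably surface. An uncommon one could easily be missed, and because r is unknown, zero reports carries no definite upper limit.

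**4. What would complete capture give?** With r = 1 and no cases, the one-sided 95% limit is 3.9% for all 75 and 1 − 0.05^(1/25) = 11.3% for one arm of 25. Even then a rate of 1.9% would not be excluded.

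**The case against.** The strongest reply is that the sponsor has addressed the risk. The animal loss has a plausible explanation in dosing volume, and it was generally without hair cell loss. A marketed otic product with nearly the same vehicle and the same 5 drops has produced no reports. This is real reassurance and belongs in any fair account. It does not close the gap, because it also rests on what was reported; the protocol mentions no hearing measurement for that product.

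Four stronger readings are tempting, and the documents do not support them.

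- *The trial cannot detect hearing loss.* It can: a complaint is recordable as an ear event with its side, and the table above shows a fair chance of at least one report in many scenarios.
- *There is no baseline record at all.* History and examination findings can hold known hearing loss; what is missing is a prompt.
- *No between-arm comparison bears on the oil.* Continued against stopped oil does, though weakly.
- *This is a first otic use in humans.* Protocol 1.1 and 1.3.1 cite earlier otic miconazole studies outside the United States.

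It is also fair to say that a question cannot match auditory brainstem responses and that the study is small and descriptive. The Investigator's Brochure, which the protocol cites for the animal study, is not among the documents and may say more.

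**Conclusion.** The point holds in a limited form. The trial can record a hearing complaint, but it cannot systematically detect hearing change, attribute it to oil or disease, or rule it out. Zero reports would be weak evidence on a risk the protocol itself raises. At the illustrative 1.9% rate the chance of any report among 75 runs from 76% with full reporting to 30% with one case in four volunteered. After zero reports the upper limit moves from 3.9% to 15.7% over the same range. These figures rest on a borrowed canine rate and assumed reporting shares. The conclusion itself does not need them: it follows from the absence of any hearing prompt. This is an inexpensive improvement to the safety objective; the efficacy analysis is not affected.

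**What to change.** Add one scripted hearing question per treated ear to the existing symptom interview.

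- **Day 1, after ear cleaning and before the first dose:** current hearing. Asked before cleaning, the relief from removing an occlusion could mask a later oil effect.
- **Each later scheduled visit, before any cleaning:** same, better or worse than that baseline (Days 8, 15 and 22, or Days 8 and 15 in the 7-day arm).
- **Recording:** enter *worse* as an adverse event with the affected ear, which Protocol 8.4 already collects.
- **Reporting:** add a row to SAP Table 14.3.2.1 giving, for each arm, the number of subjects with worsened hearing. Show it alongside the same-visit debris score so that occlusion can be considered.

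How sites manage a subject who reports worsening is for the sponsor to state.

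The cost is a short protocol amendment, one eCRF item at existing visits and one table row; no audiometry or extra visit is needed. Self-report finds only change that the subject notices, and it cannot by itself separate vehicle from disease. Prompting will also raise complaint counts relative to spontaneous-report data from other products, so the report should state how the events were elicited.
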